12.10 STUDY DISCONTINUATION

GTx, Inc. reserves the right to discontinue this study under the conditions specified in the clinical study agreement.

12.11 INDEMNITY

The Sponsor certifies that it has taken out a liability insurance policy that is consistent with the requirements for which the study is being conducted. This insurance policy is in accordance with local laws and requirements. An insurance certificate will be provided to the PI requiring this document. The insurance of the Sponsor does not relieve the PI and the collaborators of any obligation to maintain their own liability insurance policy as required by applicable law.

13. DATA HANDLING AND RECORD KEEPING

The Investigator is responsible to ensure the accuracy, completeness, legibility, and timeliness of the source data. All source documents should be completed in a neat, legible manner to ensure accurate interpretation of data. Dark ink is required to ensure clarity of reproduced copies. When making changes or corrections, cross out the original entry with a single line, and initial and date the change. DO NOT ERASE, OVERWRITE, OR USE CORRECTION FLUID OR TAPE ON THE ORIGINAL.

Copies of the CRF will be provided for use as source documents and maintained for recording data for each subject enrolled in the study. Data reported in the CRF derived from source documents should be consistent with the source documents or the discrepancies should be explained.

Study records will be maintained in locked offices with access limited to authorized individuals. Each participant will be given an identification number that will be used to enter the data into a password protected database and for the analysis.

13.1 DATA CAPTURE METHODS

13.1.1 DATA COLLECTION

Study specific data will be collected on paper case report forms (CRFs). Completed questionnaires and voiding diaries will be used as source documents, and these documents will be kept in the study files. Blank data fields should be noted as unknown (UNK) or not applicable (NA) if source information is not available or data not collected. While completing the questionnaire, if a subject leaves a question blank, it will be deemed permanently missing. All CRFs will be maintained at the study site for the length of time as determined by the IRB and federal regulations and as provided in the site's clinical study agreement. Data will be entered into a password protected electronic database that does not contain subject identifiers. Identifiers linked to unique Study ID will be kept separately from the study data. Data entry will be reviewed for accuracy.

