Statistical Considerations:	
This is a proof of concept feasibility study, so no power calculation is needed. Therefore, up to 35 subjects meeting inclusion/exclusion criteria will be recruited until 30 subjects have completed treatment. Descriptive statistics will be performed to explore changes in primary and secondary outcomes measures between baseline and end of treatment. The primary efficacy measure will be a reduction in the number of stress incontinence episodes/day. Secondary efficacy measures will include reduction in number of voids per day, volume of voids, 24 hour pad weight, responses to validated questionnaires, changes in UPP measures, changes in sexual function, and changes in pelvic floor muscles as measured by MRI.
 
Safety will be determined by the number and type of adverse events reported during treatment. Various imputation methods may be explored.

Study Intervention/Treatment:	
Participation in this study includes 5 in person study visits and two telephone and/or mailed questionnaire visits. Additional in person and/or telephone visits may be added as needed.
 
Study subjects will receive 3 mg of GTx-024 orally daily.

Table 1. Schedule of Measures.

	Screening Visit Days -21-0	Additional Screening Days -21-0	Visit 1. Baseline³ Week 0	Visit 2. Week 1 ± 3 days	Visit 3. Week 4 ± 3 days	Visit 4. Week 8 ± 3 days	Visit 5. Week 12 ± 3 days	Visit 6. Week 16 ± 7 days
	Clinic Visit	Clinic Visit	Clinic Visit	Phone Call	Clinic Visit	Clinic Visit	Clinic Visit	Phone Call and Mail
Consent	x							
Inclusion/Exclusion	x		x					
History			x					
Interview/Vital Signs	x		x		x	x	x	
Height/Weight	x				x	x	x	
24 hour Pad Weight	Instruct		x		x	x	x	
3 day Voiding Diary	Instruct		x		x	x	x	
Serum AST, ALT, Total Bilirubin	x				x	x	x	
Serum FSH ¹ ,	x							
CBC			x				x	
UA Dipstick (with culture as needed)	x		x				x	
Lipid Panel			x				x	
Testosterone Levels			x				x	
SHBG			x				x	
UPP			x				x	
Pelvic MRI		x					x	
Bladder Stress Test	x						x	
Mammogram ²		x						
Begin Daily ⁴ Treatment			x					
End Treatment							x	
Concomitant Meds	x		x	x	x	x	x	x
Adverse Events			x	x	x	x	x	x
HIV, Hep A, B, C Testing	x							
UDI-6; IIQ			x		x	x	x	x
PGI-S			x		x	x	x	x
MESA Questionnaire	x				x	x	x	x
PGI-I					x	x	x	x
FSFI Questionnaire			x		x	x	x	x
Bladder Scan PVR			x		x	x	x	
Ciprofloxacin 500 mg po (or equivalent)			x				x	
Focused Physical Exam			x				x	

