10. STATISTICAL CONSIDERATIONS

Since this is a proof of concept feasibility study, no power calculation is needed. Based on Dalton, 2011, 10-20% of patients may withdraw from the study before completing treatment. Therefore, we will recruit up to 35 patients meeting inclusion/exclusion criteria until 30 subjects have completed treatment. Descriptive statistics will be used to explore changes in primary and secondary outcomes measures between baseline and end of treatment. Although the primary efficacy measure will be a change in frequency of daily stress leaks between Baseline and Week 14 weeks, response to treatment will also consider secondary efficacy measures (change in frequency of voids per day, urine volume per void, change in 24 hour pad weight, responses to validated questionnaires, changes in UPP measures, changes in sexual function), and change in pelvic floor muscles as measured by MRI. Safety will be reported by the number and type of adverse events reported during treatment. No imputations for missing data will be conducted. There will be no adjustment for multiple testing.

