10.1 STATISTICAL METHODS

Primary end point

- The average number of episodes per day of leaking (SUI) will be calculated by summing the number of episodes over the 3 day period and dividing by 3, the change from Baseline to Week 12 will be computed and this change will be summarized with descriptive statistics (min, max, median, mean, standard deviation) and analyzed for a significant change from Baseline using the Exact Wilcoxon sign rank test.

Secondary end points

- The average number of voids per day will be calculated by summing the number of voids over the 3 day period and dividing by 3, the change from Baseline to Week 12 will be computed and this change will be summarized with descriptive statistics (min, max, median, mean, standard deviation) and analyzed for a significant change from Baseline using the Exact Wilcoxon sign rank test.
- The average volume per void will be calculated by summing the total urine amount over the 3 day period and dividing by the total number of voids recorded over 3 days, the change from Baseline to Week 12 will be computed and this

change will be summarized with descriptive statistics (min, max, median, mean, standard deviation) and analyzed for a significant change from Baseline using the Exact Wilcoxon sign rank test.

- Change in maximum urethral closure pressure measurements from Baseline to Week 12 will be computed and this change will be summarized with descriptive statistics (min, max, median, mean, standard deviation) and analyzed for a significant change from Baseline using the Exact Wilcoxon sign rank test.
- Change in 24 hour pad weight from Baseline to Week 12 will be computed and this change will be summarized with descriptive statistics (min, max, median, mean, standard deviation) and analyzed for a significant change from Baseline using the Exact Wilcoxon sign rank test.
- Change in total score on the stress incontinence section of the MESA Urinary Questionnaire from Baseline to Week 12 will be computed and this change will be summarized with descriptive statistics (min, max, median, mean, standard deviation) and analyzed for a significant change from Baseline using the Exact Wilcoxon sign rank test.

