- Change in Patient Global Impression of Severity (PGI-S) Scale from Baseline to Week 12 will be computed and this change will be summarized with descriptive statistics (min, max, median, mean, standard deviation) and analyzed for a significant change from Baseline using the Exact Wilcoxon sign rank test.
- Patient Global Impression of Improvement (PGI-I) Scale at Week 12. Descriptive statistics, (min, max, median, mean, standard deviation) will summarize these scores.
- Change in total score on the Urinary Distress Inventory (UDI-6) from Baseline to Week 12 will be computed and this change will be summarized with descriptive statistics (min, max, median, mean, standard deviation) and analyzed for a significant change from Baseline using the Exact Wilcoxon sign rank test.
- Change in total score on the Incontinence Impact Questionnaire (IIQ-7) from Baseline to Week 12 will be computed and this change will be summarized with descriptive statistics (min, max, median, mean, standard deviation) and analyzed for a significant change from Baseline using the Exact Wilcoxon sign rank test.
- Change in total score on the Female Sexual Function Index (FSFI) as well as the change in subdomain scores: libido, arousal, lubrication, orgasm, satisfaction, and pain from Baseline to Week 12 will be computed and these changes will be summarized with descriptive statistics (min, max, median, mean, standard deviation) and analyzed for a significant change from Baseline using the Exact Wilcoxon sign rank test.

- Changes in pelvic floor muscles from Baseline to Week 12 will be summarized with descriptive statistics (min, max, median, mean, standard deviation) and analyzed for a significant change from Baseline using the Exact Wilcoxon sign rank test.
- Qualitative changes in pelvic muscles will be described as decreased, increased or no change at Week 12 relative to Baseline.

Exploratory Analyses

Changes from baseline to each of the assessment times prior to Week 12 for the above endpoints will be explored, described and tested for significance using the same analytical methods noted for the primary and secondary objectives above. Durability treatment will be assessed by evaluating changes in study measures between week 12 and 16 (end of study). There will be no adjustment for multiple testing, nor will any data be imputed.

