Repeated measures (mixed models) will be used to examine the change over time by incorporating all available assessment times to test for a significant non-zero slope over time and estimate that slope and its standard error.

Various imputation methods may be explored if any of the above analyses indicate promise for the compound in the treatment of SUI. These imputation methods may allow for better estimation of effect size and consequently sample size estimation in future trials.

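### Blank questionnaire items cannot be recovered under the plan's wording and no scoring rule covers them, so paired totals on four secondary instruments may be lost avoidably

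*Combined protocol and SAP*

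**What the plan says.** Section 13.1.1 (Data Collection) states that "if a subject leaves a question blank, it will be deemed permanently missing". The sentence applies at the moment the form is being filled in and makes no provision for asking the woman about the gap. The opening of Section 13 makes the investigator responsible for the completeness of source data, and Section 13.2 requires every data point requested on the CRF to be recorded.

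On missing data, Section 10 says "No imputations for missing data will be conducted". Section 10.1 repeats this for the visit-wise and durability analyses: "There will be no adjustment for multiple testing, nor will any data be imputed". Two places leave room for later work. Section 10.1 ends with "Various imputation methods may be explored if any of the above analyses indicate promise for the compound in the treatment of SUI", and the Protocol Summary says, without a condition, "Various imputation methods may be explored". Neither names a method or says whether single items are covered.

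Section 10.1 analyses totals: "Change in total score on the stress incontinence section of the MESA Urinary Questionnaire from Baseline to Week 12 will be computed", "Change in total score on the Incontinence Impact Questionnaire (IIQ-7) from Baseline to Week 12 will be computed", and likewise for UDI-6 and for FSFI with its six subdomains. Section 8 and Appendices A, C and D give no rule for a total when an item is blank.

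**The concern.** A change score needs a total at both visits, and a total needs either every item or a rule for the missing ones. The plan closes off recovery of the answer, does not impute in the planned analyses, and supplies no rule. What happens to a woman with one blank is then decided by whoever writes the analysis program, possibly after the data are seen.

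Some blanks can be foreseen from the forms. FSFI item 15 asks about the sexual relationship with a partner but, unlike items 3 to 14 and 17 to 19, offers no option for women to whom it does not apply. A woman without a partner has no fitting answer, and she is likely to leave the same gap at both visits. Such women need not resemble the rest.

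At stake are paired observations on four patient-reported secondary instruments in a study aiming for 30 completers. A question asked before she leaves the clinic could have kept many of them.

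**Working it through.** **Inputs from the documents.** Items per total: MESA stress 9 and FSFI 19 (Section 8), UDI-6 6 and IIQ-7 7 (Appendix C). Completers: 30 (Section 10).

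**Input assumed.** The documents give no blank rate. I take q = 0.5%, 1% and 2% per item, independent across items and visits.

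**The plan's own figure.** Appendix A prints a MESA stress maximum of 27 and an urge maximum of 18. These reproduce as 9 × 3 = 27 and 6 × 3 = 18. Both denominators are fixed and make no allowance for a blank.

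**Loss if any blank removes the total.** With m items at each of two visits, the share of paired totals lost is 1 − (1 − q)^(2m). For UDI-6 at 0.5% this is 1 − 0.995^12 = 5.8%. For FSFI at 2% it is 1 − 0.98^38 = 53.6%.

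| Scale (m) | Lost, q = 0.5% | Lost, q = 1% | Lost, q = 2% | Kept of 30 (0.5% / 1% / 2%) |
|---|---|---|---|---|
| UDI-6 (6) | 5.8% | 11.4% | 21.5% | 28.2 / 26.6 / 23.5 |
| IIQ-7 (7) | 6.8% | 13.1% | 24.6% | 28.0 / 26.1 / 22.6 |
| MESA stress (9) | 8.6% | 16.5% | 30.5% | 27.4 / 25.0 / 20.9 |
| FSFI total (19) | 17.3% | 31.7% | 53.6% | 24.8 / 20.5 / 13.9 |

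**Effect of clustering.** Suppose each woman skips exactly the same items at both visits. The exponent falls from 2m to m. UDI-6 losses become 1 − 0.995^6 = 3.0% at 0.5% and 1 − 0.98^6 = 11.4% at 2%. FSFI losses become 1 − 0.995^19 = 9.1% and 1 − 0.98^19 = 31.9%. Concentration of blanks in a few women lowers the losses further.

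**Effect of a half-answered rule.** If a total is scored when at least half the items are answered, expected paired totals are 30 × [P(blanks ≤ floor(m/2))]². Even at an assumed q = 5%, this gives 29.998 for MESA stress, 29.995 for UDI-6 and 29.988 for IIQ-7. I do not apply this rule across all 19 FSFI items, for the reason given under the fix.

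**The case against.** The strongest reply is that the documents nowhere say a total is lost when an item is blank. They are silent, and prorating from answered items is not named as excluded. That is correct, which is why the loss is stated as something that may happen.

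A reader might go further and infer that imputation is forbidden outright. It is not: the Summary and the end of Section 10.1 both allow it to be explored. But that permission names no method, and in Section 10.1 it depends on promising results, so it does not define the planned totals.

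A reader might also infer that blanks will be summed as 0, so that a Week 12 blank imitates improvement. On raw sums of the printed codes one blank could move a total by up to 4/24 = 16.7% on UDI-6 and 4/28 = 14.3% on IIQ-7, and by 3/27 = 11.1% on MESA stress. The documents do not support this as the plan's method. Counting a blank as 0 would conflict with Section 13.1.1, which calls it missing. The shift also arises only if the true answer was above 0. For FSFI no item codes are printed, so no such bias can be derived.

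Other points stand in part. Most FSFI items offer a no-activity option, every MESA item offers a never option, and every UDI-6 and IIQ-7 item has a bottom category, so few blanks should come from inapplicable questions. The repeated-measures models use all available visits, so a blank at one visit does not remove the woman from them. A blank FSFI item affects its own subdomain and the total, not the other subdomains. Not querying blanks is a defensible way to avoid prompting in an open-label study, but the plan does not give that reason.

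**Conclusion.** The point holds as a limited one. The plan treats a skipped item as unrecoverable, does not impute in its planned analyses, and has no rule for scoring around the gap. A blank at Baseline or Week 12 may therefore cost a woman's change in total score on MESA stress, UDI-6, IIQ-7 or FSFI.

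The size depends on two assumptions: a blank rate that the documents do not give, and independence of blanks, which makes the loss larger than clustering would. At 0.5% to 2% per item the loss is about 6% to 22% of UDI-6 pairs and 17% to 54% of FSFI pairs.

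It would be wrong to infer that the main result is at risk. The primary endpoint comes from the voiding diary, PGI-S and PGI-I are single items, and the study is descriptive with no power calculation. No stated sample size changes. The change is still worth making, because it prevents avoidable loss at very little cost and settles the scoring before analysis.

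**What to change.** **Section 13.1.1.** Replace the sentence on blanks with a neutral completeness check of each form before the woman leaves the Baseline, Week 4, Week 8 and Week 12 clinic visits. Table 1 places the first MESA form at Screening, so that form needs the check there. She may answer or mark the item as declined, and an item counts as missing only after the check. Week 16 forms are mailed and play no part in the Baseline-to-Week 12 change, so they need no such step.

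**Section 10.1.** State that:
- a MESA stress, UDI-6 or IIQ-7 total is prorated (mean of answered items × number of items) when at least half the items are answered, and is otherwise missing;
- FSFI blanks are handled within each subdomain, and the total is computed only when all six subdomains can be scored. Section 8 scores subdomains separately, and a half rule over 19 items could fill a whole subdomain, such as the three pain items, from unrelated ones;
- a blank is never summed as 0;
- this item-level scoring is not the imputation barred in Section 10.

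The Summary's sentence on imputation should be reconciled with Section 10 in the same edit.

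**Cost.** Wording in two sections and about a minute of staff time per form. There is a small risk that prompted answers differ from unprompted ones in an open-label study, which neutral wording and the option to decline would limit.

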13.2 STUDY SITE RESPONSIBILITIES

All data requested on the CRF must be recorded. Data will be transcribed by authorized personnel at the study site from the source documents into the CRF for enrolled subjects. All information on the CRF must be traceable to these source documents. All electronic entries (including any changes or updates) will be traceable through the system. Only the PI or authorized staff may enter or modify data in the database using their unique password. The Investigator must certify that the data entered in the CRFs are complete and accurate by electronically signing the CRF.

13.3 CRF TIMING/REPORTS

A final report for the study will be completed upon completion of the study and the analysis of data. Please see information concerning publication policy (Section 14).

13.4 STUDY RECORDS RETENTION

Study documents must be retained for a minimum of 2 years after the last approval of a marketing application in an ICH region and until there are no pending or contemplated marketing applications in an ICH region or until at least 2 years have elapsed since the formal discontinuation of clinical development of the investigational product. These documents will be retained for a longer period, however, if required by local regulations. No records will be destroyed without the written consent of GTx, Inc., if applicable. It is the responsibility of GTx, Inc. to inform the PI when these documents no longer need to be retained.

13.5 PROTOCOL DEVIATIONS

A protocol deviation is any noncompliance with the clinical trial protocol that affects a subject's safety and primary efficacy, GCP, or Manual of Procedures requirements. The noncompliance may be either on the part of the subject, the PI, or the study site staff. As a result of deviations, corrective actions are to be developed by the site and implemented promptly.

These practices are consistent with ICH E6:

- 4.5 Compliance with Protocol, sections 4.5.1, 4.5.2, and 4.5.3
- 5.1 Quality Assurance and Quality Control, section 5.1.1
- 5.20 Noncompliance, sections 5.20.1 and 5.20.2

It is the responsibility of the site to use continuous vigilance to identify and report deviations within 5 working days of identification of the protocol deviation. All deviations from the protocol must be addressed in study subject source documents. A completed copy of the Protocol Deviation Form will be maintained in the regulatory file, as well as in the subject's source document. Protocol deviations will be sent to the local IRB/IEC per their guidelines. The PI/study staff is responsible for knowing and adhering to their IRB/IEC requirements.

14. PUBLICATION POLICY

Following completion of the study, it is expected some Investigators may wish to publish the results of this research in scientific journal(s). Publication rights are governed by the investigatory site's clinical trial agreement with GTx, Inc. The Investigator may request to publish this study in a scientific journal, but must have written authorization of GTx, Inc.

The data generated by this study are confidential information and the property of GTx, Inc. This confidential information may be published only in collaboration with participating personnel from GTx, Inc. or upon GTx's written consent, or otherwise under terms of the investigatory site's clinical trial agreement with GTx, Inc. All unpublished information shall not be disclosed to any third parties without the prior written consent of GTx, Inc.

The International Committee of Medical Journal Editors member journals have adopted a trials-registration policy as a condition for publication. This policy requires that all clinical trials be registered in a public trials registry such as *ClinicalTrials.gov*, which is sponsored by the U.S. National Library of Medicine. It is GTx's responsibility to register this trial in an acceptable registry.

1. APPENDIX A: MESA URINARY QUESTIONNAIRE

MESA Urinary Questionnaire				
NAME (printed): _____				
1.	Over the past three months, have you had urine loss beyond your control? Yes No			
2.	How long ago did your urine loss start? Years Months Days			
Urge Incontinence				
1.	Some people receive very little warning and suddenly find that they are losing, or about to lose, urine beyond their control. How often does this happen to you?			
	Often	Sometimes	Rarely	Never
2.	If you can't find a toilet or find a toilet that is occupied and you have an urge to urinate, how often do you end up losing urine and wetting yourself?			
	Often	Sometimes	Rarely	Never
3.	Do you lose urine when you suddenly have the feeling that your bladder is full?			
	Often	Sometimes	Rarely	Never
4.	Does washing your hands cause you to urinate?			
	Often	Sometimes	Rarely	Never
5.	Does cold weather cause you to lose urine?			
	Often	Sometimes	Rarely	Never
6.	Does drinking cold beverages cause you to lose urine?			
	Often	Sometimes	Rarely	Never
Stress Incontinence				
1.	Does coughing gently cause you to lose urine?			
	Often	Sometimes	Rarely	Never
2.	Does coughing hard cause you to lose urine?			
	Often	Sometimes	Rarely	Never

Protocol: GTx-024 as a Treatment for Stress Urinary
Incontinence in Women: A Proof of Concept Study

Compound No.: GTx-024
Author: _____

3.	Does sneezing cause you to lose urine?	Often	Sometimes	Rarely	Never
4.	Does lifting things cause you to lose urine?	Often	Sometimes	Rarely	Never
5.	Does bending over cause you to lose urine?	Often	Sometimes	Rarely	Never
6.	Does laughing cause you to lose urine?	Often	Sometimes	Rarely	Never
7.	Does walking briskly cause you to lose urine?	Often	Sometimes	Rarely	Never
8.	Does straining, if you are constipated, cause you to lose urine?	Often	Sometimes	Rarely	Never
9.	Does getting up from a sitting to a standing position cause you to lose urine?	Often	Sometimes	Rarely	Never

Protocol: GTx-024 as a Treatment for Stress Urinary Incontinence in Women: A Proof of Concept Study	Compound No.: GTx-024 Author: _____
---	--

Total Calculator:

URGE SYMPTOM INDEX LOOK-UP TABLE				
1/18 = 6%	5/18 = 28%	9/18 = 50%	13/18 = 72%	17/18 = 94%
2/18 = 11%	6/18 = 33%	10/18 = 56%	14/18 = 78%	18/18 = 100%
3/18 = 17%	7/18 = 39%	11/18 = 61%	15/18 = 83%	
4/18 = 22%	8/18 = 44%	12/18 = 67%	16/18 = 89%	

Total Score _____/18

STRESS SYMPTOM INDEX LOOK-UP TABLE						
1/27 = 4%	5/27 = 19%	9/27 = 33%	13/27 = 48%	17/27 = 63%	21/27 = 78%	25/27 = 93%
2/27 = 7%	6/27 = 22%	10/27 = 37%	14/27 = 52%	18/27 = 67%	22/27 = 81%	26/27 = 96%
3/27 = 11%	7/27 = 26%	11/27 = 41%	15/27 = 56%	19/27 = 70%	23/27 = 85%	27/27 = 100%
4/27 = 15%	8/27 = 30%	12/27 = 44%	16/27 = 59%	20/27 = 74%	24/27 = 89%	

Total Score _____/27

2. APPENDIX B: PATIENT GLOBAL IMPRESSION OF SEVERITY (PGI-S) SCALE AND PATIENT GLOBAL IMPRESSION OF IMPROVEMENT (PGI-I) SCALE

Patient Global Impression of Severity (PGI-S) Scale

Check the one number that best describes how your urinary tract condition is now.

1. Normal
2. Mild
3. Moderate
4. Severe

Patient Global Impression of Improvement (PGI-I) Scale

Check the one number that best describes how your urinary tract condition is now, compared with how it was before you began taking medication in this study.

1. Very much better
2. Much better
3. A little better
4. No change
5. A little worse
6. Much worse
7. Very much worse

3. APPENDIX C: URINARY DISTRESS INVENTORY (UDI-6) AND INCONTINENCE IMPACT QUESTIONNAIRE (IIQ-7)

Urinary Distress Inventory (UDI-6)

1. Do you experience, and, if so, how much are you bothered by frequent urination?

Not at all **0** *Slightly* **1** *Moderately* **3** *Greatly***4**

2. Do you experience, and, if so, how much are you bothered by urine leakage related to the feeling of urgency?

Not at all **0** *Slightly* **1** *Moderately* **3** *Greatly***4**

3. Do you experience, and, if so, how much are you bothered by urine leakage related to physical activity, coughing, or sneezing?

Not at all **0** *Slightly* **1** *Moderately* **3** *Greatly***4**

4. Do you experience, and, if so, how much are you bothered by small amounts of urine leakage (drops)?

Not at all **0** *Slightly* **1** *Moderately* **3** *Greatly***4**

5. Do you experience, and, if so, how much are you bothered by difficulty emptying your bladder?

Not at all **0** *Slightly* **1** *Moderately* **3** *Greatly***4**

6. Do you experience, and, if so, how much are you bothered by pain or discomfort in the lower abdominal or genital area?

Not at all **0** *Slightly* **1** *Moderately* **3** *Greatly***4**

Incontinence Impact Questionnaire (IIQ-7)

7. Has urine leakage affected your ability to do household chores (cooking, cleaning, laundry, etc)?

Not at all **0** *Slightly* **1** *Moderately* **3** *Greatly***4**

8. Has urine leakage affected your physical recreation such as walking, swimming, or other exercise?

Not at all **0** *Slightly* **1** *Moderately* **3** *Greatly***4**

9. Has urine leakage affected your entertainment activities (movies, concerts, etc.)?

Not at all **0** *Slightly* **1** *Moderately* **3** *Greatly***4**

10. Has urine leakage affected your ability to travel by car or bus more than 30 minutes from home?

Not at all **0** *Slightly* **1** *Moderately* **3** *Greatly***4**

11. Has urine leakage affected your participation in social activities outside your house?

Not at all **0** *Slightly* **1** *Moderately* **3** *Greatly***4**

12. Has urine leakage affected your emotional health (nervousness, depression, etc.)?

Not at all **0** *Slightly* **1** *Moderately* **3** *Greatly***4**

13. Has urine leakage affected your feeling frustrated?

Not at all **0** *Slightly* **1** *Moderately* **3** *Greatly***4**

14. Total Score for UDI-6= _____

15. Total Score for IIQ-7= _____

